2.4.2 Prior, concomitant and post therapies

Prior anti-cancer therapy

The number and percentage of patients who received any prior anti-neoplastic medications, prior checkpoint inhibitor therapy, prior anti-neoplastic radiotherapy prior anti-neoplastic surgery, or other therapies not defined by the previous categories, will be summarized by treatment arm. Prior anti-neoplastic medications will be summarized by therapy type (e.g. chemotherapy, hormonal therapy, immunotherapy etc.), setting (e.g. adjuvant, metastatic, etc.) and also by lowest Anatomical Therapeutic Classification (ATC) class, preferred term and treatment. Summaries will include total number of regimens, time from last treatment to progression for the last therapy, and type of therapy received as last therapy for unresectable and metastatic melanoma prior to enrollment (checkpoint inhibitor vs targeted therapy). Also, the prior checkpoint inhibitor therapy will be summarized by type of checkpoint inhibitor therapy (Anti-PD-1, Anti-CTLA-4, and combination therapy of anti-CTLA-4 and anti-PD-1). The medication therapy type of any combination therapy will be classified based on the following order: immunotherapy, chemotherapy, biologic therapy (other than immunotherapy), targeted therapy, hormonal therapy. For example, a combination therapy of chemotherapy and immunotherapy will be classified as ‘immunotherapy’. For radiotherapy, time since last

radiotherapy, locations and setting of last therapy will be summarized. For prior surgery, time since last surgery and procedure will be summarized.

Separate listings will be produced for prior anti-neoplastic medications, radiotherapy, and surgery.

Anti-neoplastic medications will be coded using the World Health Organization (WHO) Drug Dictionary (WHO-DD); anti-neoplastic surgery will be coded using MedDRA. Details regarding MedDRA and WHO-DD version will be included in the footnote in the tables/listings.

The above analyses will be performed using the FAS.

Post treatment anti-cancer therapy

Anti-neoplastic therapies since discontinuation of study treatment will be listed and summarized by ATC class, preferred term, overall and by treatment group by means of frequency counts and percentages using FAS.

The number and percentages who reported taking at least one anti-neoplastic therapy since discontinuation of study treatment by category (see [Table 2-7](#)) will be summarized by treatment group.

Table 2-7	Categories of anti-neoplastic therapies since discontinuation
Category	Sub-category
Immunotherapy	Anti-CTLA-4
	Anti-PD-1/Anti-PD-L1
	Combination Anti-CTLA-4 + Anti-PD-1/Anti-PD-L1
	IL-2
	Interferon
	Other or investigational
Targeted therapy	
Chemotherapy	
Radiotherapy	
Surgery	
Other or investigational	

Concomitant medications

Concomitant therapy is defined as all interventions (therapeutic treatments and procedures) other than the study treatment administered to a patient coinciding with the study treatment period. Concomitant therapy include medications (other than study drugs) starting on or after the start date of study treatment or medications starting prior to the start date of study treatment and continuing after the start date of study treatment.

Concomitant medications will be coded using the World Health Organization (WHO) Drug Reference Listing (DRL) dictionary that employs the WHO Anatomical Therapeutic Chemical (ATC) classification system and summarized by lowest ATC class and preferred term using

frequency counts and percentages. Surgical and medical procedures will be coded using MedDRA and summarized by SOC and preferred term. Concomitant medications with immunosuppressive intent will be summarized by lowest ATC class and preferred term using frequency counts and percentages.

All reported systemic steroids will be summarized by lowest ATC class and preferred term using frequency counts and percentages. Reported cumulative dose and maximum cumulative dose, adjusted for relative anti-inflammatory potency [Schimmer and Parker 1996], will also be summarized along with route of administration.

Table 2-8 Systemic steroid anti-inflammatory potency relative to Hydrocortisone

Steroid Name	Anti-inflammatory potency, relative to Hydrocortisone
Hydrocortisone	1
Cortisone acetate	0.8
Prednisone	4
Prednisolone	4
Methylprednisolone	5
Dexamethasone	30

All summaries will include:

1. Medications starting on or after the start of study treatment but no later than 30 days after last dose of study treatment and
2. Medications starting prior to start of study treatment and continuing after the start of study treatment.

Additional summaries will be provided to report medications starting between 31 days after last dose of study treatment and 150 days after last dose of PDR001.

Note: If a patient starts a post-treatment antineoplastic therapy after the last administration of study treatment, only medications relative to the AEs/SAEs that are reported are collected up to 150 days after discontinuation of PDR001/placebo. Medications starting between 31 days after last dose of study treatment and 150 days after last dose of PDR001 will be summarized acknowledging that complete collection of data may not be feasible for each patient.

All reported concomitant therapies will be listed. Any concomitant therapies starting and ending prior to the start of study treatment or starting more than 150 days after the last dose of PDR001 or 30 days after last dose of study treatment whichever comes last, will be flagged in the listing. The safety set will be used for all concomitant medication tables and listings.

2.5 Analysis of the primary objective

The primary objective is to demonstrate the antitumor activity of spartalizumab in combination with novel agents as measured by ORR in previously treated unresectable or metastatic melanoma patients.

2.5.1 Primary endpoint

Confirmed ORR is defined as the proportion of patients with confirmed best overall response (BOR) of complete response (CR) or partial response (PR) according to RECIST 1.1 (see Appendix 2 of the protocol). For the primary analysis, ORR will be calculated based on the FAS using local investigators review of tumor assessment data. ORR will be summarized using descriptive statistics (N,%) along with 2-sided exact 95% confidence interval (CI) [Clopper and Pearson 1934]. Tumor assessments performed before the start of any further antineoplastic therapy (i.e. any additional secondary antineoplastic therapy or surgery) will be considered in the assessment of BOR. Limited-field palliative radiotherapy may be allowed after documented discussion with Novartis (see Section 6.4.4 of the protocol). For patients who receive limited-field palliative therapy, this therapy should not be considered in determining anti-neoplastic therapy usage.

2.5.2 Statistical hypothesis, model, and method of analysis

Part 1: Selection Phase

No formal hypothesis testing will be conducted in part 1. The objective of this part of the study is to explore the anti-tumor activity of the combination of spartalizumab with novel agents as measured by ORR per RECIST v1.1, and to select an arm(s) with promising efficacy that will be advanced to the expansion phase.

To determine whether arms have the potential to demonstrate clinically meaningful response rates, arms will need to show that they cross a specific efficacy probability threshold during the selection phase to advance to the expansion phase. Conversely, arms can also be shown to cross a specific futility probability threshold and consequently will be declared as futile and enrollment in those arms will be terminated. These thresholds and probabilities are highlighted in Table 2-9.

Table 2-9 Probabilities thresholds used to declare efficacy or futility for an arm

Decision rule	Action
$P(\text{ORR} \leq 15\%) \geq 70\%$	Drop arm for futility
$P(\text{ORR} \geq 20\%) \geq 70\%$	Efficacy declared; Advance arm to expansion phase (part 2)

The futility decision rule was determined based on simulations such that arms with response rate that is not considered clinically meaningful (i.e. $\text{ORR} < 10\%$) will be dropped with high probability (as illustrated in Table 10-7 of the protocol). Similarly, the decision criterion for advancement to the expansion phase was determined so that arms with clinically meaningful response rate that warrants further development (i.e. $\text{ORR} > 25\%$) will be advanced with high probability ('power') (see also Table 10-7 of the protocol).

To calculate these probabilities, a beta-binomial posterior distribution will be used as shown below:

$$p_i \sim \text{beta}(y_i + 1, n_i - y_i + 1)$$

where y_i are the number of confirmed responses in a combination arm (i), and n_i are the number of subjects enrolled in a combination arm (i). In calculation of the posterior distribution, the uniform prior, Beta[1,1] will be taken into account for each arm. The posterior probability will be calculated separately for each arm based on the observed ORR based on RECIST v1.1 criteria at each decision point, i.e. at each interim analysis as described in Section 10.7 of the protocol.

No formal comparisons will be made between the combination arms for ORR in this ‘selection’ phase; instead each of the arms will be evaluated against efficacy and futility thresholds as presented above.

The final decision on whether an arm will be selected for advancement to the expansion phase will primarily be based on the observed ORR using decision rule described above but other efficacy (in particular duration of response), safety, and biomarker data will be considered as well. Further considerations related to the design and execution of the selection phase will be captured in the [\[SAP Technical Appendix\]](#).

Part 2: Expansion Phase

For the arms which show promise for efficacy in part 1 (based on pre-defined criteria), these arms will be expanded. After completion of the expansion phase and within each arm separately, the following statistical hypothesis will be tested based on objective response rate (ORR):

- The null hypothesis is that the response rate is not clinically meaningful ($\leq 10\%$).
- The alternative hypothesis is that the response rate is clinically meaningful ($>10\%$). The target response rate that warrants further development is $\geq 25\%$

The null hypothesis will be formally rejected if the lower bound of exact 95% CI for ORR is above 10%. **The primary analysis of ORR at the end of part 2 will be based on a combined pool of part 1 and part 2 data for any given arm.**

For example, assuming 24 subjects enrolled in an arm of interest in part 1 (see Section 10.8 of the protocol for details), assuming this arm met criteria for expansion and finally assuming 50 subjects are enrolled in the expansion phase, then combined among 74 subjects enrolled in this arm in total and followed sufficiently, 14 or more responses need to be observed to reject the null hypothesis. With those 14 responders among 74 subjects, the point estimate for ORR will be 18.9% with an exact 95% confidence interval of (10.8%, 29.7%). Since the lower bound of the exact 95% CI will be $> 10\%$, this leads to rejection of null hypothesis. The exact 95% CIs for potential observed ORR in 74 subjects are shown in [Table 2-10](#):

Table 2-10 **Exact binomial 95% confidence intervals around potential observed ORR for N=74**

Number of responders	Observed ORR (%)	95% exact CI (%)
10	13.5	6.7, 23.5
11	14.9	7.7, 25.0
12	16.2	8.7, 26.6
13	17.6	9.7, 28.2
14	18.9	10.8, 29.7

Number of responders	Observed ORR (%)	95% exact CI (%)
15	20.3	11.8, 31.2
16	21.6	12.9, 32.7
17	23.0	14.0, 34.2
18	24.3	15.1, 35.7
19	25.7	16.2, 37.2
20	27.0	17.4, 38.6
21	28.4	18.5, 40.1
22	29.7	19.7, 41.5
23	31.1	20.8, 42.9
24	32.4	22.0, 44.3

Fifty subjects enrolled in the expansion phase considered in the example above also correspond to the number of subjects needed to ensure that the hypothesis to be tested after completion of part 2 has sufficient predictive power conditioned on the ORR observed in the selection phase (part 1) (see Section 10.8 of the protocol).

Alpha Control Considerations

For each arm (treatment combination cohort) included in the study, the potential for alpha inflation arises from the adaptive nature of the design, and in particular, from the presence of a selection process based on probabilistic decision rules described in [Table 2-9](#).

To assess whether alpha is controlled for each combination treatment separately, simulations were conducted. Below in [Table 2-11](#), simulation results for scenarios that include one or more arms with the true ORR of 0.10 corresponding to the null hypothesis threshold (see also Scenarios 1 and 2 in presented in Section 10.8 of the protocol), are presented. Scenario 2 is investigated to assess a potential impact of shrinkage estimator on type I error inflation. In simulations, the focus was on assessing type I error for each ‘null hypothesis’ arm separately defined as the proportion of significant results after completion of part 2 for given arm (successful arm). The technical details for the simulations are summarized in the [\[SAP Technical Appendix\]](#).

As shown in [Table 2-11](#), for each of the ‘null hypothesis’ arms with the true ORR = 0.10, the probability is less than 0.025 (ranging between 0.0093 and 0.0126) and therefore alpha is well-controlled. Even though there no explicit alpha control measure used, alpha within each arm is still well-controlled due to the use of the futility criterion in the selection phase, as well as the adaptive nature of the sample size of part 2, based on the shrinkage estimator. Further simulation results for alpha for other scenarios and under a wide variety of samples sizes for the expansion arm will be presented in the [\[SAP Technical Appendix\]](#).

Table 2-11 Type I error assessment: Probability of a successful result for scenario where the true ORR equals 0.10 for each arm and sample size of the expansion arm is 50 subjects

Scenario	Arm	True ORR	Probability of significant result
1	1	0.10	0.0093
1	2	0.10	0.0114

1	3	0.10	0.0093
2	1	0.10	0.0126
2	2	0.25	NA*
2	3	0.25	NA*

* NA = not applicable in the context of type I error assessment; applicable only to the arms with true ORR = 0.10 corresponding to the null hypothesis.

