1.1.3 Timing of interim analyses and design adaptations

The first interim analysis will be conducted in part 1 after approximately 10 subjects have been enrolled in each of the first three arms and have completed the second post-baseline tumor assessment or have discontinued study prior to completing the second post-baseline tumor assessment. The requirement to have at least 10 subjects in each arm is based on simulations showing that 10 is the minimal number of subjects to be able to declare futility as per decision rules presented below and also in Section 10.4.2 of the protocol. If more combination arms are added to the study via future protocol amendments, those combination arms would also have their 1st interim analysis after approximately 10 subjects have been enrolled. Timing of subsequent interim analyses for part 1 and statistical thresholds are further discussed in Section 4.2 of the protocol and Section 10.4.2 of the protocol, respectively. [13621010910464462Statistical_hypo](#)No interim analysis is planned for part 2.

Figure 1-1 presents pre-specified criteria for decision-making in the selection phase.

Figure 1-1 Pre-specified criteria for decision making at each decision point (interim analysis) in part 1 to determine expansion in part 2 or drop of a combination arm

[figure not shown]

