2.1 Data analysis general information

All analysis will be performed by Novartis and/or a designated CRO. SAS version 9.4 or later software will be used to perform all data analyses and to generate tables, figures and listings. Analysis using Rshiny apps might also be used as needed.

Data included in the analysis

The analysis cut-off date for the primary analysis of study data will be established after all randomized patients in the expansion arm have either completed nine months of follow-up or have discontinued study. For the selection phase, interim analyses will be conducted once the 1st 10 subjects have been enrolled in each of the 1st three arms and then conducted approximately every 20 weeks thereafter. No formal interim analysis for efficacy will be conducted for combination arms in the expansion phase.

For each of the analyses, all statistical analyses will be performed using all data collected in the database up to the data cut-off date. All data with an assessment date or event start date (e.g. vital sign assessment date or start date of an adverse event) prior to or on the cut-off date will be included in the analysis. Any data collected beyond the cut-off date will not be included in the analysis and will not be used for any derivations.

All events with start date before or on the cut-off date and end date after the cut-off date will be reported as 'ongoing'. The same rule will be applied to events starting before or on the cut-off date and not having documented end date. This approach applies, in particular, to adverse event and concomitant medication reports. For these cases, the end date will not be imputed and therefore will not appear in the listings.

The analysis cutoff date for the final analysis of study data will be established at the end of the study defined as the earliest occurrence of one of the following:

- All subjects have died or discontinued from the study
- Another clinical study (i.e. rollover study) becomes available that can continue to provide the appropriate combination treatment in this subject population and all subjects ongoing are eligible to be transferred to that clinical study

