2.5.3 Handling of missing values/censoring/discontinuations

Patients with unknown or missing best overall response (BOR) will be counted as failures, i.e. non-responders. Patients who were non-responders before initiation of subsequent anti-cancer therapy will still be non-responders. If there is no baseline tumor assessment, all post-baseline overall lesion responses are expected to be 'Unknown'. If no valid post-baseline tumor assessments are available, the best overall response must be "Unknown" unless progression is reported. For the computation of ORR, these patients will be included in the FAS and will be counted as 'failures'.

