2.14 Interim analysis

Primary endpoint: Objective Response Rate (ORR)

Part 1: Selection phase

The 1st interim analysis is planned once at least ten patients have been randomized into each of the three initial treatment combination arms, and have completed at least 20 weeks of treatment (corresponding to two post-baseline assessments) or discontinued the study. It is possible to terminate one or more combination arms at the 1st interim analyses for lack of adequate efficacy, i.e. futility. It is also possible for advance one or more combination arms at the 1st interim analysis to the expansion phase if those arms cross a specific efficacy probability threshold.

Assessment of futility and efficacy will be based on the calculated Bayesian predictive probabilities of occurrence, using the following criteria highlighted in [Table 2-9](#).

The (posterior) predictive distribution of future responders conditioned on the observed data at the interim is a beta-binomial distribution. More details on the (posterior) predictive distribution used for this study are highlighted in [Section 2.5.2](#).

Enrollment and assessment at subsequent interim analyses for each treatment group will continue at an assessment period as defined in Section 4.2 of the protocol, or 45 subjects have been randomized into a treatment group rules presented in [Section 2.5.2](#).

Note: If new combination arms are added to the study, those combination arms will have their interim analyses at the same time-points as the first three combination arms on this study (after 10 patients have been randomized and have sufficient data for analysis, and then if needed, at an assessment period as defined in Section 4.2 of the protocol, or 45 patients have been randomized into each arm).

Part 2: Expansion phase

No formal interim analysis is planned for this part of the trial. The primary analysis will be performed once the expanded arm has fully enrolled and also after all patients randomized in the expansion phase had at least 9 months of follow-up. This timing would allow for a potential minimum duration of response of 6 months for all subjects randomized. Formal

hypothesis testing of the primary endpoint (as described in [Section 2.5.2](#)) will be performed at the primary analysis. The final analysis will be performed at the end of the study as described in [Section 2.5.1](#).

3 Sample size calculation

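### The interim posterior sets confirmed responses against all enrolled subjects, so subjects too recent to have a confirmed response can count as failures

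*SAP*

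**What the plan says.** In Part 1 each arm is judged on a Beta(y_i + 1, n_i − y_i + 1) posterior. Main SAP Section 2.5.2 states that "y_i are the number of confirmed responses in a combination arm (i"), that "n_i are the number of subjects enrolled in a combination arm (i"), and that "the uniform prior, Beta[1,1] will be taken into account for each arm". Table 2-9 drops an arm if P(ORR ≤ 15%) is at least 70% and advances it if P(ORR ≥ 20%) is at least 70%.

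Follow-up appears only in the timing of the looks. Section 1.1.3 sets the first look for when about 10 subjects per arm "have completed the second post-baseline tumor assessment or have discontinued study prior to completing the second post-baseline tumor assessment". Section 2.14 words the same trigger as subjects who "have completed at least 20 weeks of treatment (corresponding to two post-baseline assessments) or discontinued the study". Section 2.1 describes the first look as 10 subjects enrolled in each of the first three arms, with no follow-up condition, and says the looks are "then conducted approximately every 20 weeks thereafter". Section 1.1.1 lets an arm go on enrolling to 45 subjects, and no pause in enrolment is stated. Section 2.5.3 adds: "Patients with unknown or missing best overall response (BOR) will be counted as failures, i.e. non-responders".

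**The concern.** A confirmed response needs two post-baseline assessments, which the plan equates with about 20 weeks. The looks are also about 20 weeks apart. A subject enrolled since the previous look is therefore in n_i at once but has almost no chance of being in y_i, and the missing-data rule turns that gap into a failure. The same applies at the first look to anyone enrolled while the first 10 subjects mature.

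At stake is the quantity that primarily decides which arms stop and which expand. The plan says that arms with ORR above 25% will advance with high probability. A denominator padded with unassessed subjects pulls the posterior down and weakens that promise. The bias is towards futility, so the type I error is not threatened. The primary analysis, with at least 9 months of follow-up, is not affected either.

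**Working it through.** **Inputs.** Posterior, prior and thresholds: main SAP Section 2.5.2 and Table 2-9. Target rate 25%: Section 2.5.2. First look at 10 assessed subjects, later looks every 20 weeks, maximum 45: Sections 1.1.1, 1.1.3, 2.1 and 2.14. The number of immature subjects at a look (k) and the accrual rate are not in the SAP; they are assumptions, shown over a range.

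**Step 1: reproduce the plan's own boundaries.** The Arm 1A SAP uses the same posterior with the 20%/70% threshold and states 5 of 20 and 9 of 40.
- 5/20: P(ORR ≥ 20%) = 0.769; 4/20 gives 0.586.
- 9/40: 0.704; 8/40 gives 0.562.

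Both stated boundaries reproduce.

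**Step 2: add immature subjects to a fixed result.**
- 3/10: P(ORR ≥ 20%) = 0.839, advance. 3/13 gives 0.698 and 3/17 gives 0.501, neither advancing.
- 1/10: P(ORR ≤ 15%) = 0.508, continue. 1/14 gives 0.681, still continue. 1/15 gives 0.716 and 1/17 gives 0.776, both drop.

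**Step 3: one look at true ORR 25%.** Let m subjects be assessed and k immature, with no confirmed response among the k. With f and e the futility and efficacy boundaries at n = m + k, P(drop) = P(Bin(m, 0.25) ≤ f) and P(advance) = P(Bin(m, 0.25) ≥ e).

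| m | k | drop if y ≤ | advance if y ≥ | P(drop) | P(advance) |
|---|---|---|---|---|---|
| 10 | 0 | 0 | 3 | 5.6% | 47.4% |
| 10 | 3 | 0 | 4 | 5.6% | 22.4% |
| 10 | 5 | 1 | 4 | 24.4% | 22.4% |
| 10 | 10 | 1 | 5 | 24.4% | 7.8% |
| 20 | 0 | 1 | 5 | 2.4% | 58.5% |
| 20 | 5 | 2 | 6 | 9.1% | 38.3% |
| 20 | 10 | 3 | 7 | 22.5% | 21.4% |

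**Step 4: all looks together.** Single-arm simulation, 40,000 runs, true ORR 25%, steady accrual, response visible at 20 weeks, first look when 10 subjects have reached 20 weeks, then every 20 weeks until 45 are assessed.

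| New subjects per arm per 20 weeks (assumed) | Drop, n = assessed | Drop, n = enrolled | Advance, n = assessed | Advance, n = enrolled |
|---|---|---|---|---|
| 3 | 11% | 17% | 80% | 70% |
| 5 | 12% | 28% | 80% | 60% |
| 7 | 11% | 31% | 79% | 55% |
| 10 | 9% | 34% | 79% | 51% |

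Repeat runs agree to within about 1 percentage point.

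**The case against.** The strongest reply is that the plan intends an assessed cohort and the wording is loose. The first look is tied to follow-up, and added arms need sufficient data before theirs. The 74-subject example in Section 2.5.2 speaks of subjects enrolled and adequately followed. Type I error points the same way: with fully assessed subjects and looks at 10, 17, 24, 31, 38 and 45, a simulation gives about 0.009, close to the 0.0093 in Table 2-11, whereas the all-enrolled version at 7 per 20 weeks gives about 0.003. This is suggestive of the intent, not proof; other arms in that table show 0.0114 and 0.0126. It does not cure the definition. A trigger says when to look, not whom to count, and the follow-up qualifier in the 74-subject example is absent from the definition of n_i.

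Several limits do stand:
- The later looks and the interim data may be specified further in protocol Sections 4.2, 10.4.2 and 10.7 and in the SAP Technical Appendix, which were not available for this check. If they are, the SAP definition still has to agree with them.
- Up to 4 immature subjects leave the first-look futility boundary at 0 responders, although the efficacy boundary moves at 3.
- Section 1.1.1 brings all available efficacy, safety and biomarker data into each decision. Section 2.5.2 does so for advancement too, while keeping the ORR rule as the primary basis.

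A reader might infer that faster-enrolling arms are penalized relative to slower ones. Section 1.1.1 randomizes the active Part 1 arms with equal probability, so concurrent arms should accrue at similar rates apart from eligibility differences; the document does not support that claim.

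**Conclusion.** The definition of n_i in main SAP Section 2.5.2 does not match that of y_i, and applied literally it biases the decision posterior downward. An active arm can then be wrongly dropped or not advanced. Over assumed accrual of 3 to 10 subjects per arm per 20 weeks and a true ORR of 25%, drop rises from about 9–12% to 17–34% and advance falls from about 80% to 51–70%. These figures rest on the literal reading of enrolled, on no confirmed response among immature subjects, and on the posterior rule alone deciding.

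A reader might go further and conclude that active arms are, as a fact, being wrongly dropped, or that the plan's stated operating characteristics are wrong. The document supports neither: the harm is conditional on accrual and on how n_i is programmed, and the Table 2-11 figures look more consistent with assessed subjects. Arm 1A is less exposed, because its SAP already states looks at 20 and 40 subjects with matching boundaries; its n is defined only as subjects treated and should be tied to those counts.

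**What to change.** - In main SAP Sections 2.5.2 and 2.14, define y_i and n_i at every look on the same cohort: all subjects in arm i randomized early enough before the cut-off to have reached the second post-baseline assessment (about 20 weeks plus the 1-week window, so about 21 weeks). Include those who discontinued earlier. Exclude anyone randomized later, whatever their outcome; admitting recent early progressors while leaving out contemporaries still on treatment would bias ORR downward again.
- Align the Section 2.1 wording of the first interim with Sections 1.1.3 and 2.14, and check that protocol Sections 4.2 and 10.7 agree.
- In the Arm 1A SAP, state that n is the first 20 and the first 40 treated subjects, to match 5/20 and 9/40.

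The cost is a few sentences and no extra patients. The newest subjects are counted one look later. Because the present trigger lets discontinuation stand in for the second assessment, the first-look cohort could fall slightly short of 10 unless the trigger is worded on the same cohort, which may delay that look a little.
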